8.7.4 Other Observations Related to Safety

Growth assessments during the dosing period and post dosing period will be summarized as AGA, SGA/Head-Spared, SGA/Symmetric, LGA at the following time points: Pre-dose, Week 1 (Days 5-7), Week 2, 4, 6, 8, 10, and Post Dosing 1 Week, Post Dosing 1, 3 6 Month, and Early Withdrawal Prior to post dosing 6 Months. Four classifications (AGA, SGA/Head-Spared, SGA/Symmetric, and LGA) according to the growth chart for males and females will be summarized and displayed. Classifications will be based on weight and head growth measurements¹³ specified in Appendix D of the protocol and the WHO standard growth charts https://www.cdc.gov/growthcharts/who_charts.htm.

Information on feeding method (bottle, breast, and tube) and content of feedings (formula or breast milk), abdominal evaluation, etc will be summarized by number and percent of subjects.

Physical examination will be summarized by the number and percent of subjects with abnormal findings at the following time points: Pre-dose, and 3 hours Post Dosing.

Vital signs (BP, HR, RR, and Temperature) will be summarized as descriptive statistics (N, mean, SD, median, 25th and 75th quartiles, minimum, and maximum) and change from baseline at the following time points: Pre-dose, 1 hour, 2, 3, 4, 8, 12, 16, 20 and 24 hours post dosing.

The number and percentage of subjects with presence of STP206 organisms in fecal samples will be summarized, and the quantity (CFU) of the STP206 organisms detected from fecal shedding will be further summarized as descriptive statistics (N, mean, SD, median, 25th and 75th quartiles, maximum, and minimum) at the following time points: Pre-dose, Week 1 Days 1- 4), Week 1 (Days 5-7), Week 2, 3, 4, 5, 6, 7, 8, 9, 10, 11, End of Dosing or Hospital Discharge, whichever occurs first.

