#### **6.3.2. Secondary Endpoints**

The secondary endpoints of the study are:

- The incidence and the severity of AEs and SAEs in STP206-treated subjects compared to control subjects from baseline through six months after the last dose of blinded study treatment
- The incidence of clinical events (NEC, sepsis/bacteremia, feeding intolerance, death, morbidity/complications of prematurity) in STP206-treated subjects compared to control subjects from baseline through hospital discharge
- The assessment of the fecal shedding of STP206 organisms in STP206-treated subjects compared to its baseline and to control subjects through the last dose of blinded study treatment

- The assessment of the changes in routine clinical parameters in STP206-treated subjects compared to control subjects at baseline through the last dose of blinded study treatment
- The assessment of the progression of standard neonatal growth parameters in STP206-treated subjects compared to control subjects through the 6-month postdosing visit.

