### **9.3. Exclusion Criteria**

1. Infants with, or at high probability for, early onset sepsis (positive blood cultures or with the expectation of empirical antimicrobial therapy for  $\geq 5$  days).
2. Infants with persistent pulmonary hypertension of the newborn (PPHN)
3. Congenital chromosomal anomalies.
4. Congenital or acquired gastrointestinal pathology that preclude feeds within 7 days after birth (e.g., cleft lip is not an exclusion criterion, but a duodenal atresia is).
5. Infants in extremis to whom no further intensive care is offered by attending neonatologist (e.g., infant being provided only hospice/comfort care).
6. Other conditions of the infant, which in the opinion of the attending neonatologist, preclude participation.
7. Positive maternal HIV status.
8. Participation in another interventional clinical trial.

9. Small for gestational age neonates, i.e. neonates that weigh less than the 10th percentile for their gestational age according to the Estimated Fetal Weight Percentile Chart in [Appendix D](#).

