### 10.3.3. Growth Assessments

The following assessments of growth will be collected:

- Head circumference (cm) using standard measuring tape
- Body length (cm) using standard measuring tape
- Body weight (g) using digital scale

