6.6 Safety Assessments

The following are the safety assessments:

- The incidence and severity of adverse events, serious adverse events, and changes in clinical parameters from baseline through six months after the last dose of blinded study treatment.
- Physical examination through six months after the last dose of the study treatment.
- Vital signs evaluation through six months after the last dose of the study treatment.
- Concomitant medications evaluations for infant through six months after the last dose of the study treatment.
- The assessment of the progression of standard neonatal growth parameters (head circumference, body length, and body weight) in STP206-treated subjects compared to control subjects through 60f corrected age.
- Number and percent of subjects with presence of STP206 organisms in fecal shedding in STP206-treated subjects compared to control subjects through the last dose of blinded study treatment

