14.3.6.1.3	Physical Exam Findings Across All Birth Weight Stratifications\Safety Population
14.3.6.2.1	Growth Assessment Classification by Birth Weight Stratification (2000 - 1501 g, 1500 – 1000 g)\Safety Population

14.3.6.2.2	Growth Assessment Classification by Birth Weight Stratification (999 - 750 g, 749 – 500 g)\Safety Population
14.3.6.2.3	Growth Assessment Classification Across All Birth Weight Stratifications\Safety Population
14.3.6.3.1	Feeding Method and Content by Birth Weight Stratification (2000 - 1501 g, 1500 – 1000 g)\Safety Population
14.3.6.3.2	Feeding Method and Content by Birth Weight Stratification (999 - 750 g, 749 – 500 g)\Safety Population
14.3.6.3.3	Feeding Method and Content Across All Birth Weight Stratifications\Safety Population
14.3.6.4.1	STP206 Organisms in Fecal Samples by Birth Weight Stratification (2000 - 1501 g, 1500 – 1000 g)\Safety Population
14.3.6.4.2	STP206 Organisms in Fecal Samples by Birth Weight Stratification (999 - 750 g, 749 – 500 g)\Safety Population
14.3.6.4.3	STP206 Organisms in Fecal Samples Across All Birth Weight Stratifications\Safety Population

NUMBER	LISTING
16.2.1.1	Study Entry and Randomization
16.2.1.2	Patient Disposition at End of Treatment
16.2.1.3	Patient Disposition at End of Study
16.2.2.1	Eligibility Criteria
16.2.2.2	Protocol Deviation
16.2.3.1	Patients Included in Per Protocol Population
16.2.3.2	Patients Included in Intent-to-Treat Population
16.2.4.1.1	Maternal Demographic and Reproductive History
16.2.4.1.2	Maternal Pregnancy and Delivery History
16.2.4.1.3	Infant Demographic and Newborn Assessments
16.2.4.2	Infant Baseline Characteristics

16.2.4.3.1	Maternal Medical History
16.2.4.3.2	Infant Medical History
16.2.4.5.1	Maternal Prior and Concomitant Medications
16.2.4.5.2	Infant Prior and Concomitant Medications
16.2.4.5.3	Infant Concurrent Treatment
16.2.5	Study Drug Exposure
16.2.6.1.1	NEC Evaluation
16.2.6.1.2	NEC Treatment
16.2.6.2.1	Sepsis, Aerobic and Anaerobic Cultures Evaluations
16.2.6.2.2	Sepsis Assessment of Gram Bacilli Result
16.2.6.3.1	Feeding Volumes and Administration
16.2.6.3.2	Feeding Tolerance Evaluation
16.2.6.4	Infant Concomitant Antibiotic Usage for Underlying Infection
16.2.6.5	Other Complications of Prematurity - BPD
16.2.6.6	Other Complications of Prematurity - IVH
16.2.6.7	Other Complications of Prematurity - ROP
16.2.6.8	Other Complications of Prematurity - Spontaneous Gastrointestinal Perforation
16.2.6.9	Other Complications of Prematurity - PDA

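### Growth is to be summarised only as four weight-by-head size classes: body length has no planned summary after birth, and weight and head circumference have no summary of values or change

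*SAP*

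**What the plan says.** - **Endpoint.** Protocol 6.3.2 lists: "The assessment of the progression of standard neonatal growth parameters in STP206-treated subjects compared to control subjects through the 6-month postdosing visit". It does not name the measures. SAP 6.6 does: "The assessment of the progression of standard neonatal growth parameters (head circumference, body length, and body weight".
- **Data collected.** Protocol 10.3.3 has weight, head circumference and length taken at growth assessments, the last as "Body length (cm) using standard measuring tape".
- **Planned analysis.** SAP 6.4.2 defines four classes (AGA, SGA/Head-Spared, SGA/Symmetric, LGA). SAP 8.7.4 applies them: "Growth assessments during the dosing period and post dosing period will be summarized as AGA, SGA/Head-Spared, SGA/Symmetric, LGA at the following time points". It adds: "Classifications will be based on weight and head growth measurements".
- **Planned outputs.** Tables 14.3.6.2.1 to 14.3.6.2.3 are all classification tables, the pooled one being "Growth Assessment Classification Across All Birth Weight Stratifications". Listing 16.2.8.5.2 holds the growth assessments.
- **Baseline.** SAP 8.4 summarises birth length and birth weight as continuous measures. Head circumference is not in that list.
- **End of Dosing.** SAP Table 4 gives this visit a growth window of 0 to 5 days after the last dose. SAP 8.7.4 uses the visit for fecal samples but not for growth.

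**The concern.** The endpoint concerns the progression of three continuous measures. The planned summary is a count of infants in categories built from two of them. An infant can gain or lose a good deal of weight or head size relative to its peers without crossing the 10th or 90th centile, and the planned tables would not show it. A difference in length between arms could not appear in any planned table.

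The document does not read as though continuous summaries were considered and rejected. SAP 8.7.4 specifies means, SDs, quartiles and change from baseline for vital signs, and continuous statistics for fecal counts. SAP 5.2 lists only the ITT definition as a change from the protocol's analyses.

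At stake is how well the trial delivers its fourth secondary objective, which is to describe growth in treated and control infants. In preterm neonates this is also a safety description.

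**Working it through.** The documents state no power or precision figure for growth, so there is none to reproduce. The check has three parts.

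**1. Tracing each measure through the SAP**

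| Measure | Named in 6.6 | Post-baseline summary of value or change | Enters the classes | Listed |
|---|---|---|---|---|
| Weight | yes | none | yes | yes |
| Head circumference | yes | none | yes | yes |
| Length | yes | none | no | yes |

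There are three planned post-baseline growth tables, all of classes, and none contains length.

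**2. Are the classes exhaustive?** Weight and head can each be below the 10th centile, between the 10th and 90th, or above the 90th, giving 3 × 3 = 9 combinations. SAP 6.4.2 defines 4. The other 9 − 4 = 5 have no class and no rule:
- weight 10th-90th with head below the 10th
- weight 10th-90th with head above the 90th
- weight below the 10th with head above the 90th
- weight above the 90th with head 10th-90th
- weight above the 90th with head below the 10th

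**3. How much weight and head information do the classes keep?** The following are assumptions, not figures from the documents: weight and head z-scores are bivariate normal with unit variances, correlation ρ is 0.5 to 0.8, and the mean z-score is 0 to −1.

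*Single cut, for reference.* For a mean shift, efficiency relative to the continuous value is φ(z_p)² / [p(1 − p)]. With p = 0.10, z = −1.2816 and φ = 0.1755, this is 0.0308 / 0.09 = 0.342, so about 66% is lost. With 30% of infants below the cut it is 0.576.

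*The planned scheme.* Take the four classes plus an unclassified remainder, with probabilities p_k. For a shift δ common to weight and head, the class information is Σ (dp_k/dδ)² / p_k. The continuous information is 2 / (1 + ρ). Their ratio is the share kept. Counting the remainder as a fifth category favours the plan, which has no such row.

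| ρ | Mean z | Share kept | Infants in no class |
|---|---|---|---|
| 0.5 | 0 | 0.435 | 20.2% |
| 0.5 | −0.5 | 0.488 | 17.7% |
| 0.5 | −1 | 0.643 | 17.9% |
| 0.7 | 0 | 0.500 | 16.0% |
| 0.7 | −0.5 | 0.542 | 13.9% |
| 0.7 | −1 | 0.668 | 13.8% |
| 0.8 | 0 | 0.534 | 13.1% |
| 0.8 | −0.5 | 0.571 | 11.4% |
| 0.8 | −1 | 0.678 | 11.2% |

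The scheme keeps 44% to 68% and loses 32% to 56%. With 8 groups of 12, or 96 infants, that is like having 0.435 × 96 ≈ 42 to 0.678 × 96 ≈ 65 of them. For a shift in head circumference alone, the classes keep 8% to 44% of the joint weight-head information. About 11% to 20% of infants fall in no class. For length the share kept is zero.

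**The case against.** The strongest reply is that this is a stated choice in a descriptive plan. SAP 6.4.2 pre-specifies the classes as a growth variable. The sample size was not determined statistically, and comparisons are exploratory. SAP 7.1 has a general rule for continuous measures, and SAP 11 allows further tables. Class counts by arm and visit do describe weight and head relative to age and sex.

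Much of this stands, and it limits the conclusion. It does not close the gap: neither the general rule nor the open table list attaches a continuous summary to any growth measure, and the classes contain no length.

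A reader might infer more than the documents support:

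- *The growth data are lost, or the objective cannot be answered.* Values are listed and tables can be added. The objective is to describe, and it is met in part.
- *Most of the information is discarded.* That fits a single 10th-centile cut or a head-only effect, but not most of the common-shift scenarios above.
- *The SGA classes are empty before dosing by design.* The exclusion in Protocol 9.3 concerns size for gestational age, on a chart of birth measurements. Dosing may start up to 96 hours after birth, and baseline is the last assessment before the first dose. SAP 8.3.3 also foresees eligibility deviations.
- *End of Dosing is the only dosing-period visit common to all infants.* The shortest intended dosing is 14 days, so Weeks 1 and 2 fall within every infant's intended dosing. End of Dosing matters for another reason: its window follows the actual last dose, so it captures each infant at the end of its own exposure.
- *All counts are in cells of 8 and 4.* That is true within a cohort. SAP 8.7 also pools strata, giving 4 × 8 = 32 infants per dose and 8 × 4 = 32 controls.

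**Conclusion.** The point holds as a mismatch between endpoint and analysis. Of the three growth measures in SAP 6.6, length has no pre-specified summary after birth, and weight and head circumference enter only through size classes. No change from baseline is specified for any of them. The End of Dosing growth window is defined but unused, and five of nine weight-by-head combinations have no class.

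The loss for weight and head is roughly one third to two thirds: 32% to 56% for the class scheme under a common shift, and 66% for a single 10th-centile cut. These figures rest on assumed normality, correlation and mean z-scores. The absence of length, the unused visit and the gaps in the classes rest on the text alone.

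The consequence is moderate, because the output is secondary, descriptive and exploratory. The change is still worth making, since the better summary uses data already collected.

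**What to change.** Before the SAP is finalised for database lock:

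1. In SAP 8.7.4 and the table list, add descriptive tables of weight (g), length (cm) and head circumference (cm): N, mean, SD, median, quartiles, minimum, maximum and change from baseline. Present them by treatment, within stratum and pooled, at every growth time point already listed and at End of Dosing.
2. Preferably add age- and sex-specific z-scores where the charts allow. Protocol Appendix D prints only 10th-90th centile ranges for weight and head, so z-scores would need the fuller reference tables, and length would need a chart that covers it.
3. Keep the four classes as supportive output, with an unclassified row so that counts sum to the infants assessed.
4. Optionally, add an exploratory adjusted treatment difference with a 95% CI. This goes beyond SAP 7.2, which plans no covariate adjustment, and the main fix does not depend on it.

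The cost of items 1 and 3 is one additional table set and one extra row, with no new data collection.

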### **6.3. Endpoints**

#### **6.3.1. Primary Endpoints**

The incidence and severity of AEs, SAEs and changes in clinical parameters in STP206-treated subjects compared to control subjects from baseline through 30 days after the last dose of blinded study treatment.

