### 10.3. Safety Procedures

#### 10.3.1. Physical Examination

Physical examinations will be performed that will include assessments of the following body systems:

- Head, Eyes, Ears, Nose, Throat (HEENT)
- Cardiovascular
- Respiratory
- Central nervous system
- Abdomen/Gastrointestinal
- Genitourinary
- Musculoskeletal
- Dermatologic/Skin

Physical examination findings will be noted in the subject medical records. The screening and Day 1 physical examinations will be recorded on a CRF for the subject. Subsequent physical examinations performed in the NICU will not be recorded on a CRF but all adverse findings meeting the definition of an AE (see [Section 12.2.1](#)), independent of relationship or severity, will be recorded on the CRF as either adverse events or complications of prematurity.

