#### 10.3.2. Vital Signs

Vitals signs will include:

- Temperatures (°C) - axillary or by skin probe
- Heart rate (BPM) - measured by auscultation
- Respiratory rate (breaths/minute) – measured by observation

- Blood pressure (mmHg) – measured by either non-invasive (oscillometric) or invasive (arterial pressure transducers) techniques
- SpO2 (pulse oximetry in %)

Vital signs will be noted in the subject medical records. The screening and Day 1 vital signs will be recorded on a CRF for the subject. If there are multiple measurements obtained as standard of care during these study days, the first assessments obtained after noon will be used for the study. The date and time of when these assessments were obtained will be recorded. Subsequent vital signs performed in the NICU will not be recorded on a CRF, but all adverse findings will be recorded on the CRF as AEs.

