16.2.7.1	Adverse Events\Safety Population
16.2.7.2	Serious Adverse Events\Safety Population
16.2.7.3	Listing of Adverse Event Leading to Discontinuation of Study Treatment\Safety Population
16.2.7.4	Listing of All Adverse Events with an Outcome of Death\Safety Population
16.2.7.5	Sterile Site Infection, Aerobic and Anaerobic Cultures Evaluation\Safety Population
16.2.8.2	Vital Signs at Week 1 Day 1 Dosing Period\Safety Population

16.2.8.4	Physical Examination at Pre-Dose and Week 1 Day 1 Dosing Period\Safety Population
16.2.8.5.1	Fecal Samples Evaluations\Safety Population
16.2.8.5.2	Growth Assessment\Safety Population

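### Change from baseline in vital signs and physical examinations, which the primary endpoint follows to 30 days after the last dose, is summarised only for the first-dose day

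*SAP*

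**What the plan says.** **Endpoints.** Protocol 6.3.1 places beside AEs and SAEs the "changes in clinical parameters in STP206-treated subjects compared to control subjects from baseline through 30 days after the last dose of blinded study treatment". Protocol 6.3.2 adds a secondary endpoint on routine clinical parameters, "compared to control subjects at baseline through the last dose of blinded study treatment". The synopsis (Criteria for Evaluation, safety variables) gives physical examinations and vital signs as the clinical items and names growth measures alongside them.

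**Data capture.** Protocol 10.3.1 and 10.3.2 put the screening and Day 1 values on the CRF. After that, "Subsequent physical examinations performed in the NICU will not be recorded on a CRF", and likewise "Subsequent vital signs performed in the NICU will not be recorded on a CRF". Adverse findings are still entered, as AEs or (for examinations) as AEs or complications of prematurity.

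**Analysis.** SAP 8.7.4 summarises vital signs and their "change from baseline at the following time points: Pre-dose, 1 hour, 2, 3, 4, 8, 12, 16, 20 and 24 hours post dosing". It summarises abnormal examination findings before dosing and 3 hours after. In SAP Table 4, the footnote for vital signs and examinations is attached only to the 1- to 24-hour rows. The planned vital-sign listing is titled "Vital Signs at Week 1 Day 1 Dosing Period", and the examination listing covers pre-dose and Day 1.

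**Conflicting statements.** SAP 6.6 names "Vital signs evaluation through six months after the last dose of the study treatment" as a safety assessment, and examinations over the same period. Protocol 13.2.3.2 commits to summarising examination findings at every time point with collected data. SAP 5.2 declares one change from the protocol analyses, the ITT definition, and does not mention this one.

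**The concern.** A named component of the primary endpoint is planned to be described only around the first dose of a product given daily for 2 to 11 weeks. A live product may act through repeated dosing, and a first-day window cannot show a gradual shift in, say, heart rate or blood pressure. Vital signs also change as preterm infants mature, so later values can be interpreted only against concurrent controls, and that comparison is not planned.

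The DSMC is to see available primary and secondary endpoint data at each escalation step. For NICU dosing after Day 1 it would have adverse findings but no CRF vital-sign or examination values. The SAP also contradicts itself, so an analyst could follow 6.6 or 8.7.4 and produce different reports.

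**Working it through.** There is no sample-size, power or alpha figure to reproduce. The check follows each measurement from schedule to report.

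**1. Which dose do the SAP hours refer to?** Protocol 11.3.2.1 schedules vital signs after the initial dose hourly for 4 hours (1, 2, 3, 4), then every 4 hours to 24 hours (8, 12, 16, 20, 24). That gives nine points, identical to the nine post-dose points in SAP 8.7.4. The 3-hour examination is also in 11.3.2.1. The SAP therefore summarises the first-dose day only.

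**2. From measurement to report (vital signs and examinations)**

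| Stage | Scheduled | On CRF | Table 4 window | Summary in 8.7.4 | Planned listing |
|---|---|---|---|---|---|
| Pre-dose and Day 1 | yes | yes | yes | yes | yes |
| Rest of dosing, in NICU | daily (11.3.1) | adverse findings only | none | none | none |
| End of dosing | yes (7.1; 11.3.2.8 if stopped early) | adverse findings only, if in NICU | none (row limited to growth and fecal sample) | none | none |
| 1 week, 1 month | yes (11.3.3) | not barred once discharged | growth only | none | none |
| 3 and 6 months | yes (11.3.3) | not barred once discharged | growth only | none | none |

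**3. Calendar coverage.** Intended dosing is 14 to 77 days (protocol Table 2).

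- Endpoint window: 14 + 30 = 44 days to 77 + 30 = 107 days.
- Vital signs: 1/44 = 2.3% to 1/107 = 0.9%.
- Examinations: 3 hours = 0.125 day; 0.125/44 = 0.28% to 0.125/107 = 0.12%.

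**4. Would adding rows under the existing windows be enough?** No. Table 4 counts post-dosing days from the expected last dose, while the endpoint counts from the last dose. Take an infant with 77 intended days whose last dose is on study day 54 (an illustration, using the Table 2 minimum with no missed days).

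- The endpoint window closes on study day 54 + 30 = 84.
- The Table 4 1-month window requires 21 to 35 for (assessment day − 77 + 1), which is study days 97 to 111.
- That is 97 − 54 = 43 to 111 − 54 = 57 days after the actual last dose, wholly outside the endpoint window.
- A visit 30 days after the actual last dose scores 84 − 77 + 1 = 8, which falls in the 1-week window (6 to 13).

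Also, the protocol's 1-month visit is on Days 30 to 35, so most of its range lies after the 30-day limit. The SAP needs to say that this visit serves as the 30-day assessment.

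**5. Precision.** A cohort of 12 randomised 2:1 has 12 × 1/3 = 4 controls and 8 treated. Over all strata there are 8 × 4 = 32 controls and 4 × 8 = 32 infants per dose. Within-cohort means will be imprecise, so the combined display matters.

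**The case against.** The strongest counter-case is that after Day 1 the protocol deliberately captures these parameters by exception. Adverse vital-sign findings go on the CRF as AEs, and so do examination findings that meet the AE definition, whatever their severity or relationship. AEs are then tabulated by treatment and stratum for six months. The study is a small descriptive Phase Ib with exploratory comparisons only. The synopsis lists safety variables and does not formally define clinical parameters. Growth is summarised to six months, and feeding and abdominal evaluations are summarised too.

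Much of this stands. A reader might infer that this part of the endpoint cannot be answered at all, or that nothing is observed after the first dose. The documents do not support either reading:

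- The CRF restriction covers NICU measurements only; values from visits after discharge are not barred.
- AE and SAE incidence and severity are unaffected.
- The protocol 12.2.1 exemption for findings expected in this population covers examination findings, not vital signs.
- SAP 11 says tables and listings may be added, and its vital-sign and examination table titles carry no time limit. It would be too strong to say that later values can never appear in any output.

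A reader might also take 0.9% to 2.3% as the share of information lost. It is a ratio of calendar days and does not measure lost information, bias or power.

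The objection does not remove the gap. The endpoint names changes in clinical parameters in addition to AEs and SAEs. An AE count cannot show a shift in mean against control. Growth is reported only as size classes. In a descriptive study the summaries are the result, so a named endpoint still has to be described.

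**Conclusion.** The concern holds as a gap between endpoint and analysis, and as an undeclared contradiction within the plan. The planned summaries of change in vital signs and examinations cover one day (vital signs) or 3 hours (examinations) of a 44- to 107-day endpoint window. The secondary endpoint on routine clinical parameters has the same gap.

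The defect has two parts. For visits after discharge it is an omission from the SAP, which added windows and rows can repair to the extent that the values are on the CRF. For the NICU period it is also a capture problem, because the values stay in the medical record.

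This rests on three assumptions: that clinical parameters means what the synopsis lists; that the separate table shells follow SAP 8.7.4; and that dosing runs for its intended length. Including growth among the clinical parameters would not close the gap for the other two. The point should be fixed. It does not invalidate the primary safety analysis.

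**What to change.** 1. **Protocol 10.3.1 and 10.3.2:** enter on the CRF the already scheduled end-of-dosing, 1-week and 1-month vital signs and examinations, even if the infant is still in the NICU. For infants already past these visits, values noted in the medical record may be retrievable.
2. **SAP 8.7.4, Table 4, tables 14.3.5.x and 14.3.6.1.x, listings 16.2.8.2 and 16.2.8.4:** add end of dosing, 1 week and 1 month, plus 3 and 6 months to match SAP 6.6. Show treatment against control by stratum and with all strata combined. For these summaries, count post-dosing windows from the actual last dose, and state that the Day 30 to 35 visit serves as the 30-day assessment.
3. **Keep the 0 to 24 hour tables**, labelled as first-dose tolerability.
4. **If the CRF change is not made**, state in the SAP that in-NICU clinical parameters after Day 1 are assessed only through AEs.

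The cost is some extra data entry at visits that already take place and more rows in existing tables, with no new procedures or patients. Within-stratum means will be imprecise at about 4 controls per cohort. Change between Day 1 and the end of dosing would still be seen only at the end, apart from AEs.
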